## 2.8 Confirmatory measurement/duration of response

### Confirmation

In non-randomized trials where response is the primary endpoint, confirmation of PR and CR is required to ensure responses identified are not the result of measurement error. In randomized trials or studies where stable disease or progression is the primary endpoints, confirmation of response is not required since it will not add value to the interpretation of trial results. In the case of SD, measurements must have met the SD criteria at least once after trial entry at a minimum interval (in general not less than 6 to 8 weeks) that is defined in the trial protocol.

### Duration of overall response

The duration of overall response is measured from the time measurement criteria are first met for CR/PR (whichever is first recorded) until the first date that recurrent or progressive disease is objectively documented (taking as reference for progressive disease the smallest measurements recorded on study). The duration of overall complete response is measured from the time measurement criteria are first met for CR until the first date that recurrent disease is objectively documented.

### Duration of stable disease

Stable disease is measured from the start of the treatment (in randomized trials, from date of randomization) until the criteria for progression are met, taking as reference the smallest sum on study (if the baseline sum is the smallest, this is the reference for calculation of PD). The clinical relevance of the duration of stable disease varies in

different studies and diseases. If the proportion of patients achieving stable disease for a minimum period of time is an endpoint of importance in a particular trial, the protocol should specify the minimum time interval required between two measurements for determination of stable disease.

Note: The duration of response and stable disease as well as the progression-free survival (PFS) are influenced by the frequency of follow-up after baseline evaluation. It is not in the scope of this guideline to define a standard follow-up frequency. The frequency should take into account many parameters including disease types and stages, treatment periodicity, and standard practice. However, these limitations of the precision of the measured endpoint should be taken into account if comparisons between trials are to be made.

## 2.9 PFS/TTP

Phase III trials in advanced cancers are increasingly designed to evaluate PFS or time to progression (TTP) as the primary outcome of interest. Assessment of progression is relatively straightforward if the protocol requires all subjects to have measurable disease. Increasingly, trials allow entry of both subjects with measurable disease as well as those with non-measurable disease only. In this circumstance, care must be taken to explicitly describe the findings which would qualify for PD for those subjects without measurable lesions. Because the date of progression is subject to ascertainment bias, the timing of investigations in study arms should be the same.

## Appendix III NCI-CTCAE 5.0 Evaluation Criteria for Toxic Side Effects of Tumor Drugs

Immune system disorders						
Adverse Event	Abbreviation	1	2	3	4	5
Allergic reaction/hypersensitivity (including drug fever)	Allergic reaction	Transient flushing or drug eruption; drug fever < 38°C (< 100.4°F)	Rash; flushing; drug eruption; dyspnea; drug fever ≥ 38°C (≥ 100.4°F)	Symptomatic bronchospasm, with or without drug eruption; intravenous administration indicated; edema/angioedema; hypotension	Allergic shock	Death
Note: Drug eruptions shown to be allergic reaction or hypersensitivity are graded as allergic reaction/hypersensitivity (including drug fever). Other considerations: Cytokine release syndrome/acute infusion reaction						
Blood/bone marrow disorders						
Hemoglobin	Hemoglobin	<LLN-6.2mmol/L <LLN-100g/L	<6.2-4.9 mmol/L <100-80 g/L	<4.9-4.0 mmol/L <80-65 g/L	<4.0 mmol/L <65 g/L	Death
White blood cells (all)	White blood cells	<LLN-3000/mm  <LLN-3.0×10  /L	<3000-2000/mm  <3.0-2.0×10  /L	<2000-1000/mm  <2.0-1.0×10  /L	<1000/mm  <1.0×10  /L	Death
Lymphopenia	Leukopenia	<LLN-800/mm  <LLN-0.8×10  /L	<800-500/mm  <0.8-0.5×10  /L	<500-200/mm  <0.5-0.2×10  /L	<200/mm  <0.2×10  /L	Death
Neutrophils/granulocytes (ANC/AGC)	Neutrophil granulocytes	<LLN-1500/mm  <LLN-1.5×10  /L	<1500-1000/mm  <1.5-1.0×10  /L	<1000-500/mm  <1.0-0.5×10  /L	<500/mm  <0.5×10  /L	Death
Platelet	Platelet	<LLN-75000/mm  <LLN-75.0×10  /L	<75000-50000/mm  <75.0-50.0×10  /L	<50000-25000/mm  <50.0-25.0×10  /L	<25000/mm  <25.0×10  /L	Death
Cardiac arrhythmia						
Supraventricular and nodal arrhythmias - Options: - Atrial fibrillation - Atrial flutter - Atrial tachycardia/paroxysmal atrial tachycardia - Nodal/junctional - Sinus arrhythmia - Sinus bradycardia - Sinus tachycardia	Supraventricular arrhythmia - Supraventricular premature beats (premature atrial contraction; premature contraction of atrioventricular node/atrioventricular junction area) - Supraventricular tachycardia	Asymptomatic, intervention not indicated	Non-urgent intervention indicated	Symptomatic and incompletely controlled medically, or controlled with device (e.g., pacemaker)	Life threatening (such as arrhythmia, hypotension, syncope, shock related to CHF)	Death

- Supraventricular arrhythmia NOS						
Overview of adverse cardiac events						
Left ventricular systolic dysfunction	Left ventricular systolic dysfunction	Asymptomatic, ejection fraction (EF) < 60%–50% and systolic fraction (SF) < 30%–24% at rest	Asymptomatic, EF < 50%–40% and SF < 24%–15% at rest	Symptomatic chronic heart failure, responsive to intervention, EF < 40%–20%; SF < 15%	Refractory chronic heart failure or poorly controlled, EF < 20%; intervention indicated, such as left ventricular assist device, left ventricular partial resection or heart transplant	Death
Systemic symptoms						
Tiredness (weakness, somnolence, listless)	Tiredness	Mild tiredness compared to baseline	Moderate tiredness, or causing difficulty in engaging in some activities of daily living (ADL)	Severe tiredness, limiting ADL	Causing disability	—
Fever (no neutropenia, which is defined as ANC < 1.0 × 10  /L)	Pyrexia	38.0–39.0°C (100.4–102.2°F)	>39.0–40.0°C (102.3–104.0°F)	> 40.0°C (> 104.0°F) for ≤ 24 h	> 40.0°C (> 104.0°F) for > 24 h	—
Weight loss	Weight loss	5% to < 10% decrease from baseline; intervention not indicated	10% to < 20% decrease from baseline; nutritional support indicated	≥ 20% decrease from baseline; tube feeding or total parenteral nutrition (TPN) indicated	—	—
Dermatosis/skin disorders						
Alopecia/atrichia (scalp or body)	Alopecia	Sparse or alopecia areata	Complete (bald)	—	—	—
Injection site reaction/extravasation change Other considerations: Allergic reaction/hypersensitivity (including drug fever); ulcer	Injection site reaction	Pain; pruritus; erythema	Pain or swelling with inflammation or phlebitis	Severe ulcer or necrosis; surgical treatment indicated	—	—
Pruritus/itchy Other considerations: Rash/peeling	Pruritus	Mild or localized	Intense or extensive	Intense or extensive, limiting ADL	—	—
Rash/peeling	Rash	Macule or papule or	Macule or papule or	Severe systemic erythroderma	Systemic exfoliative,	Death

Note: Rash/peeling may be used for GVHD		erythema, without associated symptoms	erythema, with pruritus or other associated symptoms; localized peeling or other lesions, < 50% body surface area (BSA)	or macula, papule or blister; peeling range ≥ 50% BSA	ulcerative or bullous dermatitis	
Gastrointestinal disorders						
Appetite loss Other considerations: Weight loss	Appetite loss	Appetite loss and unchanged eating habits	Oral intake changed, with no significant weight loss or malnutrition; oral nutritional supplementation indicated	Causing significant weight loss or malnutrition (e.g., inadequate oral intake of calories and/or fluids); intravenous (IV) infusion, tube feeding, or TPN indicated	Life threatening consequences	Death
Colitis Other considerations: Bleeding, GI-Option	Colitis	Asymptomatic, pathological or radiological changes only	Abdominal pain, blood or mucus in stool	Abdominal pain, fever, change in bowel habits with ileus; peritoneal signs	Life threatening consequences (such as perforation, bleeding, ischaemia, necrosis, toxic megacolon)	Death
Diarrhea Note: Diarrhea includes those of small bowel or colonic origin, and/or ostomy diarrhea Other considerations: Dehydration; hypotension	Diarrhea	An increase in the number of bowel movements per day of < 4 times and a mild increase in ostomy output from baseline	An increase in the number of bowel movements per day of 4–6 times from baseline; IV infusion < 24 h; moderate increase in ostomy output from baseline; not limiting ADL	An increase in the number of bowel movements per day of ≥ 7 times ; fecal incontinence; IV infusion ≥ 24 h; hospitalization; severe increase in ostomy output from baseline; limiting ADL	Life-threatening consequences (e.g., hemodynamic compromise)	Death
Mucositis/stomatitis (clinical examination) - Options: - Anus - Esophagus - Large intestine - Larynx - Oral cavity	Mucositis (clinical examination) - Options - Pharynx - Rectum - Small intestine - Stomach - Trachea	Mucosal erythema	Patchy ulceration or pseudomembrane formation	Confluent ulcer or pseudomembrane formation; minor post-traumatic hemorrhage	Tissue necrosis; massive spontaneous hemorrhage; life-threatening consequences	Death
Nausea	Nausea	Appetite loss and	Reduced oral intake	Inadequate oral intake of	Life threatening	Death

Other considerations: appetite loss; vomiting		unchanged eating habits	without significant weight loss, dehydration, or malnutrition; IV infusion for < 24 h indicated	calories or fluids; IV infusion, tube feeding, or TPN for ≥ 24 h indicated	consequences	
Vomiting Other considerations: Dehydration	Vomiting	1 episode within 24 hours	2 to 5 episodes within 24 hours; IV infusion for < 24 h indicated	≥ 6 episodes within 24 hours; IV infusion or TPN for ≥ 24 h indicated	Life threatening consequences	Death
Hepatobiliary disorders						
Hepatic dysfunction/failure (clinical)	Hepatic dysfunction	—	Jaundice	Biliary tremor	Hepatic encephalopathy or coma	Death
Note: Jaundice is not an AE, but it can occur with hepatic dysfunction or bile duct obstruction and is graded as a result of hepatic dysfunction/failure or increased bilirubin. Other considerations: Bilirubin (hyperbilirubinemia)						
Nervous system disorders						
Peripheral neuropathy (disease involving the peripheral nerves (sixth cranial nerve))		Asymptomatic, clinical or diagnostic observations only, intervention not indicated	Moderate symptoms: limiting instrumental ADL	Severe symptoms: limiting self-care ADL	—	—
Infections						
Febrile neutropenia (fever of unknown origin without clinically or microbiologically documented infection) (ANC < 1.0 × 10  /L, fever ≥ 38.5°C)	Febrile neutropenia	—	—	Existence of symptoms	Life-threatening consequences (e.g., septic shock, hypotension, acidosis, necrosis)	Death
Other considerations: Neutrophils/granulocytes (ANC/AGC)						
Infections (clinically or microbiologically documented) with Grade 3 or 4 neutrophils (ANC < 1.0 × 10  /L)	Infections (clinically documented)	—	Localized; local intervention indicated	IV antibiotic, antifungal, or antiviral intervention indicated; radiologic or operative intervention indicated	Life-threatening consequences (e.g., septic shock, hypotension, acidosis, necrosis)	Death
Note: Fever without documented infection with grade 3 or 4 neutrophils is graded as febrile neutropenia (fever of unknown origin without clinically or microbiologically documented infection) Other considerations: Neutrophils/granulocytes (ANC/AGC)						
Metabolism disorders						
Acidosis (metabolic or respiratory)	Acidosis	7.3 ≤ PH < normal value	—	pH<7.3	PH < 7.3 with life-threatening	Death

					consequences	
Albumin, low serum level (hypoalbuminaemia)	Hypoalbuminaemia	<LLN-3g/dL <LLN-30g/L	<3-2g/dL <30-20g/L	<2g/dL <20g/L	—	Death
ALT, SGPT (serum glutamic-pyruvic transaminase)	ALT	>ULN-2.5×ULN	>2.5-5.0×ULN	>5.0-20.0×ULN	>20.0×ULN	—
AST, SGOT (serum glutamic oxaloacetic transaminase)	AST	>ULN-2.5×ULN	>2.5-5.0×ULN	>5.0-20.0×ULN	>20.0×ULN	—
Bilirubin (hyperbilirubinemia)		>ULN-1.5×ULN	>1.5-3.0×ULN	>3.0-10.0×ULN	>10.0×ULN	—
Creatinine	Creatinine	>ULN-1.5×ULN	>1.5-3.0×ULN	>3.0-6.0×ULN	>6.0×ULN	
Note: For pediatric patients, adjust according to age-appropriate levels Other considerations: Glomerular filtration rate						
GGT (gamma-glutamyl transpeptidase)	GGT	>ULN-2.5×ULN	>2.5-5.0×ULN	>5.0-20.0×ULN	>20.0×ULN	—
Proteinuria	Proteinuria	1 + or 0.15–1.0 g/24 h	2 + to 3 + or > 1.0–3.5 g/24 h	4 + or 3.5 g/24 h	Nephrotic syndrome	Death
Pain						
Pain	Pain	Mild pain, not affecting function	Moderate pain: Pain or pain medication affects function but not ADL	Severe pain: Pain or pain medication severely affects ADL	Causing disability	—
Lung/upper respiratory tract disorders						
Pulmonary fibrosis (radiographic changes)	Pulmonary fibrosis	Minor radiographic changes (or patchy or bilateral basal lung changes), with < 25% of the entire lung volume estimated to be fibrotic based on radiographic findings.	Patchy or bilateral basal lung changes, with 25% to < 50% of the entire lung volume estimated to be fibrotic based on radiographic findings.	Intensive or extensive infiltration/consolidation, with 50% to < 75% of the entire lung volume estimated to be fibrotic based on radiographic findings.	≥ 75% of the entire lung volume is estimated to be fibrotic based on radiographic findings; honeycomb changes	Death
Note: Pulmonary fibrosis is usually a "late effect" found after 3 months of radiotherapy or multimodal combination therapy (including surgery). Pulmonary fibrosis is considered to be scarring/fibrotic lung tissue and is difficult to differentiate from pneumonia, which is usually seen within 3 months of radiotherapy or multimodal combination therapy. Other considerations: Adult respiratory distress syndrome (ARDS); cough; dyspnea (air hunger); hypoxia; infection (clinically or microbiologically documented) with grade 3 or 4 neutrophils (ANC < 1.0 × 10  /L) - Option: Infection with normal ANC or Grade 1 or 2 neutrophils - Option: Infection with unspecified ANC-Option						
Syndrome						
Influenza-like syndrome	Influenza-like syndrome	Symptomatic but not affecting function	Moderate or causing difficulty for patients to engage in some ADL	Severe symptoms, limiting ADL	Causing disability	Death

Note: Influenza-like syndrome represents a collection of symptoms, including cough with catarrhal symptoms, fever, headache, listless, muscular soreness, and frailty, and is used when a collection of symptoms occurs with a single pathophysiological change.

Vascular disorders

Phlebitis (including superficial thrombosis)	Phlebitis	—	Existence of symptoms	—	—	—
Other considerations: Injection site reaction/altered extravasation						

Ear and labyrinth disorders					
Adverse Event	Grade 1	Grade 2	Grade 3	Grade 4	Grade 5
Hearing impaired (damage to ear structures, causing partial or complete loss of sound perception or comprehension)	
Adults enrolled on a monitoring program (a 1, 2, 3, 4, 6, and 8 kHz audiogram): Threshold shift of 15–25 dB averaged at 2 continuous test frequencies in at least one ear or subjective change in the absence of a Grade 1 threshold shift.
 
Pediatrics (a 1, 2, 3, 4, 6 and 8 kHz audiogram): >20 dB at any frequency tested or does not meet criteria for > Grade 2
	
Adults enrolled on a monitoring program (a 1, 2, 3, 4, 6, and 8 kHz audiogram): Threshold shift of > 25 dB averaged at 2 continuous test frequencies in at least one ear.
 
Adults not enrolled in monitoring program: Hearing loss with hearing aid or intervention not indicated; limiting instrumental ADL
 
Pediatrics (a 1, 2, 3, 4, 6 and 8 kHz audiogram): > 20 dB at > 4 kHz
	
Adults enrolled on a monitoring program (a 1, 2, 3, 4, 6, and 8 kHz audiogram): Threshold shift of > 25 dB averaged at 3 continuous test frequencies in at least one ear; intervention indicated
 
Adults not enrolled in monitoring program: Hearing loss with hearing aid or intervention indicated; limiting self-care ADL
 
Pediatrics (a 1, 2, 3, 4, 6 and 8 kHz audiogram): Hearing loss sufficient to indicate therapeutic intervention, including hearing aids; > 20 dB at 3 kHz and above in one ear; additional speech-language related services indicated
	
Adults: Profound bilateral hearing loss (> 80 dB at 2 kHz and above); non-serviceable hearing
 
Pediatrics: Audiologic indication for cochlear implant and additional speech-language related services indicated
	—
Middle ear inflammation (inflammation and redness of the middle ear)	Serous otitis	Serous otitis: Medical intervention indicated	Mastoiditis: Necrosis of canal soft tissue or bone	Life-threatening: Urgent intervention indicated	Death
Tinnitus (disorder characterized by noise in ears, such as ringing, buzzing, roaring, or cracking)	Mild symptoms; intervention not indicated	Moderate symptoms: Limiting instrumental ADL	Severe symptoms: Limiting self-care ADL	—	—
Vertigo (a sensation as if the external world were revolving around the patient or as if he himself were revolving in space)	Mild symptoms	Moderate symptoms: Limiting instrumental ADL	Severe symptoms: Limiting self-care ADL	—	—

## **Appendix IV ECOG Scoring Criteria for Patient Quality of Life Evaluation**

0	Normal activities
1	Mild symptoms, capable of all self-care and restricted in physically strenuous activity
2	Tolerable tumor symptoms, capable of all self-care, but < 50% in bed during the day
3	Severe tumor symptoms, > 50% in bed during the day but not bedbound, and capable of only limited self-care
4	Bed bound
5	Death

## Appendix V FACT-H&N (V4) Quality of Life Questionnaire

The following reflect the conditions of patients with diseases similar to yours. Think back to your past 7 days and tick the number that best matches your condition. There is no right or wrong answer, please answer all questions intuitively

Physical well-being (**PWB**) in the past 7 days:

GP1 I had low energy

0. Not at all    1. A little bit                  2. Somewhat                  3. Quite a bit                  4. Very much

GP2 I had nausea

0. Not at all    1. A little bit                  2. Somewhat                  3. Quite a bit                  4. Very much

GP3 It was difficult for me to meet the needs of my family because of my poor health

0. Not at all    1. A little bit                  2. Somewhat                  3. Quite a bit                  4. Very much

GP4 I had pain

0. Not at all    1. A little bit                  2. Somewhat                  3. Quite a bit                  4. Very much

GP5 I was affected by side effects of treatment

0. Not at all    1. A little bit                  2. Somewhat                  3. Quite a bit                  4. Very much

GP6 Generally, I felt like a patient

0. Not at all    1. A little bit                  2. Somewhat                  3. Quite a bit                  4. Very much

GP7 I had to be in bed

0. Not at all    1. A little bit                  2. Somewhat                  3. Quite a bit                  4. Very much

Social/Family well-being (**SWB**) in the past 7 days:

GS1 I felt close to my friends

0. Not at all    1. A little bit                  2. Somewhat                  3. Quite a bit                  4. Very much

GS2 I got emotional support from my family

0. Not at all    1. A little bit                  2. Somewhat                  3. Quite a bit                  4. Very much

GS3 I got support from my friends and neighbors

0. Not at all    1. A little bit                  2. Somewhat                  3. Quite a bit                  4. Very much

GS4 My family understood my illness

0. Not at all    1. A little bit                  2. Somewhat                  3. Quite a bit                  4. Very much

GS5 I was satisfied with family communication about my illness

0. Not at all    1. A little bit                  2. Somewhat                  3. Quite a bit                  4. Very much

If you have a partner or have sex, please answer items 13 and 14, otherwise, you can leave it blank.

GS6 I felt close to my partner

0. Not at all    1. A little bit                  2. Somewhat                  3. Quite a bit                  4. Very much

GS7 I was satisfied with my sex life

0. Not at all    1. A little bit                  2. Somewhat                  3. Quite a bit                  4. Very much

Emotional well-being (**EWB**) in the past 7 days:

GE1 I felt sad

0. Not at all                                      1. A little bit                                      2. Somewhat                                      3. Quite a bit                                      4. Very much

GE2 I was satisfied with my ability to cope with the disease

0. Not at all                                      1. A little bit                                      2. Somewhat                                      3. Quite a bit                                      4. Very much

GE3 I am losing hope in the fight against my illness

0. Not at all                                      1. A little bit                                      2. Somewhat                                      3. Quite a bit                                      4. Very much

GE4 I felt nervous

0. Not at all                                      1. A little bit                                      2. Somewhat                                      3. Quite a bit                                      4. Very much

GE5 I was worried about dying

0. Not at all                                      1. A little bit                                      2. Somewhat                                      3. Quite a bit                                      4. Very much

GE6 I worried that my disease would get worse

0. Not at all                                      1. A little bit                                      2. Somewhat                                      3. Quite a bit                                      4. Very much

Functional well-being (**FWB**) in the past 7 days:

GF1 I was able to work (including housework)

0. Not at all                                      1. A little bit                                      2. Somewhat                                      3. Quite a bit                                      4. Very much

GF2 My work (including housework) was fulfilling

0. Not at all                                      1. A little bit                                      2. Somewhat                                      3. Quite a bit                                      4. Very much

GF3 I was able to enjoy life

0. Not at all                                      1. A little bit                                      2. Somewhat                                      3. Quite a bit                                      4. Very much

GF4 I had accepted my illness

0. Not at all                                      1. A little bit                                      2. Somewhat                                      3. Quite a bit                                      4. Very much

GF5 I slept well

0. Not at all                                      1. A little bit                                      2. Somewhat                                      3. Quite a bit                                      4. Very much

GF6 I was enjoying the things I usually do for fun

0. Not at all                                      1. A little bit                                      2. Somewhat                                      3. Quite a bit                                      4. Very much

GF7 I was content with my quality of life right now

0. Not at all                                      1. A little bit                                      2. Somewhat                                      3. Quite a bit                                      4. Very much

Additional questions (**FACT-HN**) in the past 7 days:

hn1 I was able to eat the foods that I like

0. Not at all                                      1. A little bit                                      2. Somewhat                                      3. Quite a bit                                      4. Very much

hn2 My mouth was dry

0. Not at all                                      1. A little bit                                      2. Somewhat                                      3. Quite a bit                                      4. Very much

hn3 I had trouble breathing

0. Not at all                                      1. A little bit                                      2. Somewhat                                      3. Quite a bit                                      4. Very much

hn4 My voice had its usual quality and strength

0. Not at all                                      1. A little bit                                      2. Somewhat                                      3. Quite a bit                                      4. Very much

hn5 I was able to eat as much food as I want

0. Not at all	1. A little bit	2. Somewhat	3. Quite a bit	4. Very much
hn6 I felt like my appearance (e.g., neck) had changed				
0. Not at all	1. A little bit	2. Somewhat	3. Quite a bit	4. Very much
hn7 I could swallow naturally and easily				
0. Not at all	1. A little bit	2. Somewhat	3. Quite a bit	4. Very much
hn8 I smoked				
0. Not at all	1. A little bit	2. Somewhat	3. Quite a bit	4. Very much
hn9 I drank alcohol (beer, wine or liquor)				
0. Not at all	1. A little bit	2. Somewhat	3. Quite a bit	4. Very much
hn10 I was able to communicate with others				
0. Not at all	1. A little bit	2. Somewhat	3. Quite a bit	4. Very much
hn11 I could eat solid foods				
0. Not at all	1. A little bit	2. Somewhat	3. Quite a bit	4. Very much

FACT-H&N Area of Scoring Method	Number of Entries	Score Range	Scoring Method
Physical well-being (PWB)	7	0–28	GP1+ GP2+ GP3+ GP4+ GP5+ GP6+ GP7
Social/Family well-being (SWB)	7	0–28	GS1+ GS2+ GS3+ GS4+ GS5+ GS6+ GS7
Emotional well-being (EWB)	6	0–24	GE1+ GE2+ GE3+ GE4+ GE5+ GE6
Functional well-being (FWB)	7	0–28	GF1+ GF2+ GF3+ GF4+ GF5+ GF6+ GF7
Functional Assessment of Cancer Therapy - General (FACT-G)	27	0–108	PWB+ SWB+ EWB+ FWB
Head and neck subscale (HNS)	9+2	0–36	hn1+hn2+hn3+hn4+hn5+hn6+hn7+hn10+hn11
Total score	38	0–144	PWB+ SWB+ EWB+ FWB+HNS

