### **2.2 Secondary Objectives**

- 1) To evaluate the long-term survival of patients.
- 2) To evaluate the quality of life of patients.

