### **2.3.2 Secondary endpoints**

- ORR, PFS, OS, CR, PR and DOR (according to RECIST v1.1)
- Safety and adverse events (according to NCI CTC AE v4.0)
- Quality of life assessment (FACT-H&N.V4 Quality of Life questionnaire)

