## **5.3 Treatment Period**

- The following assessments should be completed before each dose in each cycle. If the test is completed within 7 days before the first dose during the screening

period, it is not required prior to the first dose.

- ✓ ECOG score;
- ✓ Vital signs: Pulse, respiratory rate, body temperature, blood pressure;
- ✓ Physical examination: General conditions, head and face, skin, lymph nodes, neck, eyes, ENT, oral cavity, respiratory system, cardiovascular system, abdomen, reproductive-urinary system, musculoskeletal system, nervous system, mental status, and others;
- ✓ Blood routine: Complete blood count and differential count (white blood cells, red blood cells, lymphocytes, monocytes, neutrophils, basophils, eosinophils, hemoglobin), platelet count;
- ✓ Clinical chemistry: ALT, AST, GGT, total bilirubin, direct bilirubin, AKP, blood urea nitrogen or urea (blood urea nitrogen is preferred), total protein, albumin, creatinine, blood glucose, lactate dehydrogenase, K+, Na+, Ca2+, Mg2+, Cl;
- ✓ EBV-DNA test;
- ✓ Urinalysis: White blood cell count, red blood cell count, urine protein. If urine protein is  $\geq 2+$ , a 24-hour urine protein test is required;
- ✓ Routine stool test: White blood cells, red blood cells, occult blood;
- ✓ Coagulation function: Prothrombin time, activated partial thromboplastin time, thrombin time, fibrinogen, D-dimer, international normalized ratio;
- ✓ Thyroid function: TSH, FT3, FT4 (FT3 and FT4 can be replaced by T3 and T4 if they are not available);
- ✓ 12-lead electrocardiogram (12-Lead ECG): Additional necessary tests should be performed according to the judgment of the investigators in case of any abnormality;
- ✓ Concomitant medication: Concomitant medication should be recorded in detail;
- ✓ AEs: AEs should be recorded in detail;
- Radiological examination (completed before dosing every two cycles): CT or MRI of the nasopharynx, neck, chest, and abdomen (including the pelvis). An enhanced scan is preferred if not contraindicated. The radiological examination should be performed every 6 weeks. For bone metastases, a bone scan is

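### The FACT-H&N formulas in Appendix V add 15 negatively worded items unreversed to 21 positively worded ones, and no visit list in Section 5 says when to give the questionnaire

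*Protocol*

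**What the plan says.** Section 2.2 of the protocol lists as a secondary objective "To evaluate the quality of life of patients". Section 2.3.2 makes the instrument a secondary endpoint: "Quality of life assessment (FACT-H&N.V4 Quality of Life questionnaire".

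Appendix V prints the items and a scoring table. All items share one response scale, 0 to 4, from not at all to very much. Some items describe something bad, for example "GP1 I had low energy". Others describe something good, for example "GF3 I was able to enjoy life". The table scores each subscale as a plain sum of its items, for example "GP1+ GP2+ GP3+ GP4+ GP5+ GP6+ GP7" for physical well-being (PWB), and gives the total as "PWB+ SWB+ EWB+ FWB+HNS" with a range of 0 to 144. The appendix does not mention reversing any item and does not say whether a high score is good or bad.

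Section 5 sets out the visit procedures. Section 5.3 opens its list with "The following assessments should be completed before each dose in each cycle" and then names performance status, vital signs, laboratory tests, ECG, concomitant medication, adverse events and imaging. The FACT-H&N is not in that list, nor in those of Sections 5.1, 5.4, 5.5 and 5.6.

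**The concern.** There are two separate faults.

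First, the printed formulas mix directions. A sum is readable only if a higher answer means the same thing on every item. Here a patient whose pain and nausea disappear loses points on PWB, FACT-G and the total, while a patient who enjoys life more gains points on functional well-being (FWB), FACT-G and the total. An analyst who applies the table as printed could report a real improvement as no change or as a decline. This is a stated rule that gives a wrong result, not a detail left for later.

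Second, a secondary endpoint has no assessment times. A site working from the Section 5 lists has no instruction to collect a baseline or an on-treatment questionnaire. The items ask about the past 7 days, so a missed assessment cannot be reconstructed later.

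**Working it through.** **Inputs.** Item wording, response scale and formulas come from Appendix V; visit lists from Sections 5.1 to 5.6. Items hn8 and hn9 (smoking and alcohol) enter no sum.

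**1. Reproduce the stated ranges.** Maximum = 4 × number of scored items:
- PWB, social/family well-being (SWB) and FWB: 4 × 7 = 28 each
- Emotional well-being (EWB): 4 × 6 = 24
- Head and neck subscale (HNS): 4 × 9 = 36
- FACT-G: 4 × 27 = 108
- Total: 4 × 36 = 144

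All agree with the table, so it has been read intact.

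**2. Classify the 36 scored items by wording.**
- Negative (4 is bad): GP1 to GP7; GE1 and GE3 to GE6; hn2, hn3 and hn6. That is 7 + 5 + 3 = 15.
- Positive (4 is good): GS1 to GS7; GE2; GF1 to GF7; hn1, hn4, hn5, hn7, hn10 and hn11. That is 7 + 1 + 7 + 6 = 21.

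**3. Score the best and worst possible health.** With the printed sum, best = 4 × positive items and worst = 4 × negative items. With negative items reversed (4 minus the answer), best = 4 × all items and worst = 0.

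| Score | Negative | Positive | Printed: best vs worst | Reversed: best vs worst |
|---|---|---|---|---|
| PWB | 7 | 0 | 0 vs 28 | 28 vs 0 |
| SWB | 0 | 7 | 28 vs 0 | 28 vs 0 |
| EWB | 5 | 1 | 4 vs 20 | 24 vs 0 |
| FWB | 0 | 7 | 28 vs 0 | 28 vs 0 |
| FACT-G | 12 | 15 | 60 vs 48 | 108 vs 0 |
| HNS | 3 | 6 | 24 vs 12 | 36 vs 0 |
| Total | 15 | 21 | 84 vs 60 | 144 vs 0 |

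PWB and EWB run opposite to SWB and FWB. The printed total separates best from worst health by 84 − 60 = 24 points instead of 144. A printed total of 144 requires the top answer to every good item and every bad item at once.

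**4. Effect on change.** Under the printed sum, change in total = (points gained on positive items) − (points of relief on negative items). Under reversed scoring the two are added.
- One category better on all 36 items: printed 21 − 15 = +6; reversed +36. For FACT-G: printed 15 − 12 = +3; reversed +27.
- Nausea (GP2) and pain (GP4) both fall from 4 to 0, all else equal: printed −8; reversed +8, in PWB, FACT-G and the total.

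The printed total therefore falls whenever symptom relief outweighs gains on the positive items.

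**5. Visit lists.**

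| Section | FACT-H&N named? |
|---|---|
| 5.1 Screening | No |
| 5.2 Enrollment | No (eligibility and dosing only) |
| 5.3 Treatment period | No |
| 5.4 Follow-up | No |
| 5.5 Early termination | No |
| 5.6 Unscheduled visits | No |

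The opening of Section 5 refers to the study schedule, but Section 10, the schedule section, holds only enrollment and follow-up dates. Section 8 does not name quality of life among the items to be recorded. ECOG status is scheduled, and the title of Appendix IV connects it with quality of life, but it is not the endpoint named in Section 2.3.2.

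**The case against.** The strongest reply concerns scope.

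- **The scoring fault is partial and repairable.** SWB and FWB are wholly positive and score correctly. PWB is wholly negative, so its plain sum is a coherent symptom score whose direction is not labelled; 28 minus the printed PWB restores it. HNS, FACT-G and the total still rank best above worst. If item-level answers are kept, reversal is arithmetic at analysis and no data are lost. All of this stands. A reader might infer that the scoring table alone makes the quality-of-life objective unanswerable; it does not.
- **The questionnaire is prescribed.** The synopsis, Section 2.3.2 and Appendix V all call for it. A reader might infer that the trial will hold no quality-of-life data at all. The protocol does not support that: what is missing is when to give the questionnaire, and sites may give it anyway. Without common times, however, such data would be hard to compare, and a missing baseline could not be replaced.
- **Blank items.** For GS6 and GS7 the appendix tells patients "If you have a partner or have sex, please answer items 13 and 14, otherwise, you can leave it blank", while the SWB sum includes both. A reader might infer a loss of up to 8 points and call for prorating. Handling of blank items is commonly left to a statistical analysis plan, 8 points is only the ceiling, and any prorating rule would have to be squared with the statement in Section 9.2 that missing data are not imputed. This is not part of the point.
- **The trial's decision is untouched.** The sample size and success rule in Section 3.2 use disease control rate only. This stands and limits the weight of the point.

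What the reply does not remove is that the protocol prints a formula that gives a wrong result, and that assessment times are a protocol matter which an analysis plan cannot supply after the event.

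**Conclusion.** The point holds on both parts. The Appendix V table is wrong as written: 15 negative items are added unreversed to 21 positive ones, PWB and EWB run backwards, and HNS (24 vs 12), FACT-G (60 vs 48) and the total (84 vs 60) are severely attenuated. Symptom relief lowers FACT-G and the total. Separately, the endpoint has no stated assessment times; this is the more serious part, because scoring can be corrected later and uncollected answers cannot.

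The result rests on two assumptions: that the direction of each item is read from its wording in Appendix V, and that no assessment schedule stands in the protocol's opening pages, which were not in the text available. The readable part of the contents list shows no such schedule.

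**What to change.** In Appendix V, score GP1 to GP7, GE1, GE3 to GE6, hn2, hn3 and hn6 as 4 minus the answer before summing, and state that a higher score means better quality of life on every subscale, FACT-G and the total. The printed ranges then hold with 0 as worst health and the maximum as best. Keep item-level answers in the case report form, because EWB and HNS cannot be corrected from their sums alone.

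Add the FACT-H&N to Section 5.1 as a baseline assessment, to Section 5.3 at fixed on-treatment times (the 6-weekly imaging visit is one convenient choice), and to Section 5.5. Leave the handling of blank GS6 and GS7 to the statistical analysis plan, reconciled there with Section 9.2.

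The cost is a few lines of protocol text and a few minutes of patient time at each of these visits.
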